## **5.3. Other Analysis Sets**

Not applicable.

## **5.4. Subgroups**

Not applicable.

# **6. ENDPOINTS AND COVARIATES**

## **6.1. Safety Endpoints**

1. *Onset state of adverse events/adverse reactions (particularly the major investigation items).*
2. *Onset state of adverse reactions and potential influencing factors (particularly the major investigation items).*
3. *Safety in patients with special background (pediatric patients, elderly patients, pregnant women, patients with renal or hepatic dysfunction).*
4. *Safety in patients with hepatic dysfunction (including the comparative examination with results from the foreign phase 1 clinical study).*
5. *Onset state of interstitial lung disease (including asymptomatic cases with imaging findings of the disease).*

6. *Potential risk factors of interstitial lung disease.*
7. *Characteristics of interstitial lung disease (imaging findings, onset timing, duration, and breakdown by severity).*
8. *List of clinical course of interstitial lung disease (contents of treatment, response to treatment, and outcome) and clinical course after the drug is restarted (presence/absence of recurrence/exacerbation, etc.).*
9. *Onset state of various related events suspected of causing interstitial lung disease (pneumonitis/lung infiltration and pulmonary fibrosis, etc.).*
10. Duration of treatment (Defined as the period from the date of initiation of treatment with this drug to the date of completion of treatment with this drug in this study. Patients for whom the completion of treatment is not reported in this study will be censored at the date of last dose.).

## 6.2. Efficacy Endpoints

1. Response rate (percentage of complete response [CR] + partial response [PR])
2. Clinical benefit rate (percentage of CR + PR + stable disease [SD] for at least 24 weeks)
3. Progression-free survival (PFS): Time from the date of initiation of treatment with this drug in this study to the date progressive disease (PD) or all-causality death is first confirmed during the treatment period (including 28 days after the completion of treatment with this drug) and the period up to the date of final evaluation of tumor response. PD or death occurring during the treatment period (including 28 days after the completion of treatment with this drug) or the period up to the date of final evaluation of tumor response, whichever period is the earlier, will be handled as a PFS event, and patients without a PFS event will be censored at the date of final evaluation of tumor response. Patients with no record on tumor response at all will be censored at the date of initiation of treatment with this drug.

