5.4 Observation period

The observation period for this study will be set until Week 24 after the start of administration (cases treated with the drug for more than 25 weeks will be included in the separately planned Special Investigation on long-term use and observed for up to 96 weeks after the start of administration)

[figure not shown]
Clinical evaluation of tumor: Weeks 8, 16, and 24. For discontinued cases, if the clinical evaluation of tumor is not performed within 4 weeks prior to discontinuation, clinical evaluation of tumor will be performed at the time of discontinuation.

Adverse events: Until Week 24 after the start of administration. If the drug is discontinued before Week 24, observe until Day 28 after the discontinuation of administration.

This study will be conducted using a case report form divided into separate booklets. The results during the following observation periods will be recorded in the different booklets of the case report form.

| Booklet | Observation period |
|------------|---|
| Booklet 01 | Start of administration to Week 4 (Day 28) |
| Booklet 02 | Week 5 (Day 29) to Week 12 (Day 84) after start of administration |
| Booklet 03 | Week 13 (Day 85) to Week 24 (Day 168) after start of administration |

(Start of administration)
(Day 1)

Observation period and evaluation time points for each booklet of case report form

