6 INVESTIGATION ITEMS AND SCHEDULE

The investigator will conduct the study according to the following schedule of observation. After the conclusion of the study contract, the investigator will register patients who meet the registration conditions, check their data including the background information at the start of administration, and fill in the case report form (at patient registration and at the start of administration). In the observation period, the investigator will check their follow-up data at the end of the observation period of each booklet of the case report form or at discontinuation when the drug is discontinued, record the data to the case report form and submit it to the sponsor.

[Observation schedule]

| | | Observation and evaluation time points | | | |
|--|--|--|--|---|--|
| | | At the start of administration | Starting date of administration to Week 4 (Day 28) | Weeks 5 to 12 after start of administration | Weeks 13 to 24 after start of administration |
| Registration information | ID number, patient initials, gender, date of birth (age), scheduled date to start administration, and availability of pre-treatment chest CT | ● | | | |
| Patient background | | ● | | | |
| Clinical history | | ● | | | |
| Prior treatment history | | ● | | | |
| Record of TORISEL treatment | | | ↔ | ↔ | ↔ |
| Concomitant therapy (drug therapy) | | | ↔ | ↔ | ↔ |
| Concomitant therapy (non-drug therapy) | | | ↔ | ↔ | ↔ |
| Examination (chest CT) | | ● | ● | ● | ● |
| Examination (chest X-rays) | | ● | ● | ● | ● |
| Examination (clinical laboratory testing) | | ● | ● | ● | ● |
| Effectiveness evaluation* | | | | Week 8 | Week 16 Week 24 |
| Pregnancy status | | | ● | ● | ● |
| Patient summary (continuation/discontinuation status) | | | ● | ● | ● |
| Adverse events | | | ↔ | ↔ | ↔ |
| Detailed information on adverse events related to interstitial lung disease (Attachment: detailed case report form) | | | ↔ | ↔ | ↔ |

* For discontinued cases, if the clinical evaluation of tumor is not performed within 4 weeks prior to discontinuation, clinical evaluation of tumor will be performed at the time of discontinuation.

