6.5 Effectiveness evaluation

6.5.1 Clinical evaluation of tumor

Clinical evaluation of tumor will be performed at Weeks 8, 16, and 24 after the start of administration. The presence/absence of the target, non-target, and new lesions will be evaluated at each evaluation time point. The evaluation will be performed using the following 4 classes with reference to the "New response evaluation criteria in solid tumours: Revised RECIST guideline (version 1.1) - Japanese Translation JCOG Version."

| | | |
|---------------------|------|---|
| Complete response | (CR) | Disappearance of all target regions |
| Partial response | (PR) | At least a 30% decrease in the sum of the longest diameter (LD) of target lesions, taking as reference the baseline sum LD |
| Progressive disease | (PD) | At least a 20% increase in the sum of the LD of target lesions, taking as reference the smallest sum LD recorded since the treatment started |
| Stable disease | (SD) | Neither sufficient shrinkage to qualify for PR nor sufficient increase to qualify for PD, taking as reference the smallest sum LD since the treatment started |

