7.2.2 Analysis for effectiveness evaluation

The response rate and clinical benefit rate as shown below will be used as main analytical items in the effectiveness analysis set. An **CCI** analysis including the examination of factors influencing effectiveness will be performed, as required.

- [1] Response rate (rate of CR + PR)
- [2] Clinical benefit rate (Rate of cases with CR + PR + SD maintained for 24 weeks or longer)

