### 8.2.7. Efficacy Analysis

- **Response rate and clinical benefit rate**

The number and percentage of patients by best overall response, the response rate and its 95% confidence interval, and the clinical benefit rate and its 95% confidence interval will be tabulated in the safety analysis set and efficacy analysis set.

The response rate is defined as the percentage of patients whose best overall response is CR or PR.

The clinical benefit rate is defined as the percentage of patients whose best overall response is CR, PR, or SD.

The best overall response is defined as the best response among recorded overall response.

Table 1 of “New Guideline for the Assessment of Treatment Effect on Solid Cancer (Response Evaluation Criteria in Solid Tumors [RECIST] Guideline)–Japan Clinical Oncology Group [JCOG] version in Japanese” will be used for overall response, but overall response based on combinations of tumor response not corresponding to the table because of unknown data and no entry of data was uniquely defined. Therefore, the

tabulation analysis is not in complete compliance with the guideline and uses the guideline for reference.

**Table 1. Overall Response Based on Combinations of Tumor Response in Target and Non-target Lesions Including the Presence or Absence of New Lesions**

Target lesion	Non-target lesion	New lesion	Overall response
HCR	CR	Absent	CR
CR	IR/SD	Absent	PR
PR	Other than PD	Absent	PR
SD	Other than PD	Absent	SD
PD	Any response	Any response	PD
Any response	PD	Any response	PD
Any response	Any response	Present	PD

The following tumor response will be converted as shown by the arrow.

Non-target lesion: Absent → CR, not entered → IR/SD.

New lesion: Not entered → absent.

Overall response not corresponding to any combination in Table 1 after the above conversion will be considered as “unassessable.”

In addition, tabulation will be performed in the same manner by category shown below.

For items using reference laboratory test values, results using corporate reference values will be tabulated separately from results using institutional reference values as necessary.

- Site of metastasis [none, lung, liver, bone, lung + 1 organ, lung + 2 organs, lung +  $\geq 3$  organs,  $\geq 2$  organs other than lung, others];
- Whether criteria for proper use are met [yes, no];

- Prior treatment history [IFN- $\alpha$ , IL-2, Sutent, Nexavar, Afinitor, others];

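### Clinical benefit requires stable disease for at least 24 weeks, which leaves no margin when the last scheduled scan is Week 24 (Day 168), and SAP 8.2.7 drops the duration condition altogether

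*SAP*

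**What the plan says.** Clinical benefit rate is one of the protocol's two main effectiveness items. It is defined three times.

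- Protocol 7.2.2: "Clinical benefit rate (Rate of cases with CR + PR + SD maintained for 24 weeks or longer".
- SAP 6.2, item 2: "Clinical benefit rate (percentage of CR + PR + stable disease [SD] for at least 24 weeks".
- SAP 8.2.7: "The clinical benefit rate is defined as the percentage of patients whose best overall response is CR, PR, or SD". The same section adds: "The best overall response is defined as the best response among recorded overall response".

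The first two set a minimum duration for SD. The third sets none.

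The evaluation schedule is in Protocol 6.5.1: "Clinical evaluation of tumor will be performed at Weeks 8, 16, and 24 after the start of administration". Protocol 5.4 takes the start of administration as Day 1 and gives the last booklet of the case report form the period "Week 13 (Day 85) to Week 24 (Day 168) after start of administration". The schedule in Protocol 6 places the Week 24 evaluation in the column "Weeks 13 to 24 after start of administration".

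Two other statements bear on later data. Protocol 5.4 sends longer-treated patients to a separate long-term surveillance with observation to 96 weeks, and SAP 8.2 pools the two data sets unless stated otherwise. The long-term objective in SAP 2.2.2 concerns safety only.

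Neither document says from when the duration of SD is counted, whether Day 1 is included, or what window applies to the Week 24 evaluation.

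**The concern.** A duration threshold should be one that a patient followed exactly to schedule can meet with some tolerance. Here the threshold equals the end of scheduled tumour follow-up, so ordinary variation in scan dates decides whether a patient who never progressed counts. The long-lasting SD that the endpoint is meant to capture is the part most exposed.

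The second problem is that SAP 8.2.7, which sets out the calculation, omits the threshold. Two analysts working from different sections would classify the same patients differently. If 8.2.7 were simply brought into line with SAP 6.2 and Protocol 7.2.2, the rule without margin would enter the reported rate. The two problems therefore need to be settled together.

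**Working it through.** **Inputs.** Day 1 = start of administration and the booklet limits (Protocol 5.4); evaluations at Weeks 8, 16 and 24 (Protocol 6.5.1); minimum SD duration of 24 weeks (Protocol 7.2.2, SAP 6.2); no minimum duration (SAP 8.2.7); 600 patients, about 35% treated to 24 weeks in the trials and 20% expected to re-register (SAP 2.1.2). I read the 24-week condition as attached to SD only, not to CR or PR.

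**Step 1: the documents' own day count.** End of week w = Day 7w. 7 × 4 = 28, 7 × 12 = 84, 7 × 24 = 168. All three match Protocol 5.4. Week 24 therefore runs from Day 7 × 23 + 1 = 162 to Day 168.

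**Step 2: duration at the last scan, timed from the start of treatment.** For a scan on Day d, inclusive duration is d/7 weeks and elapsed duration is (d − 1)/7 weeks.

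| Scan day | Inclusive (weeks) | Elapsed (weeks) | At least 24 weeks? |
|---|---|---|---|
| 162 | 23.14 | 23.00 | no on either count |
| 165 | 23.57 | 23.43 | no on either count |
| 167 | 23.86 | 23.71 | no on either count |
| 168 | 24.00 | 23.86 | inclusive only |
| 169 | 24.14 | 24.00 | yes, but after the booklet closes |

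Within the last booklet (Days 85-168) there is one qualifying day with inclusive counting and none with elapsed time.

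**Step 3: the other possible starting point.** If SD is timed from the first evaluation that shows it, with Week 8 on Day 56, the Week 24 scan gives (168 − 56)/7 = 16 weeks. Nobody would qualify within the all patient surveillance.

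**Step 4: the definitions side by side**, timed from the start of treatment, with no evaluation after Day 168.

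| Patient | Protocol 7.2.2 and SAP 6.2 | SAP 8.2.7 |
|---|---|---|
| SD at Weeks 8, 16 and 24, last scan Day 168 | depends on the counting rule | benefit |
| SD at Weeks 8, 16 and 24, last scan Day 165 | not benefit | benefit |
| SD at Week 8, PD at Week 16 | not benefit | benefit |

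The second row is the missing margin. The third is a plain conflict between definitions, whatever the scan dates.

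**Step 5: what can be said about size.** 600 × 0.20 = 120 patients expected to re-register; 600 × 0.35 = 210 if the trial figure for treatment to 24 weeks applied. Patients in the second row must come from those followed to Week 24, so these figures bound that row only. They include patients with CR or PR, who qualify anyway. Patients in the third row may have stopped earlier and are not bounded by them.

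**The case against.** The strongest reply has four parts.

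1. A reader might infer that patients stable at every evaluation cannot qualify. The documents do not support that. On the protocol's own convention Day 168 is Week 24, and a scan on that day meets the threshold. An ordinary reader may also take 24 weeks of SD to mean SD still present at the Week 24 evaluation. Both points stand. But that reading is not written down, and a literal derivation would reject a scan on Days 162-167.

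2. A reader might infer that the rate falls toward the response rate. Under SAP 8.2.7 as written it would not, because any SD counts. This also stands: the loss arises only where the 24-week wording is applied. The conflict between sections remains, and it decides which result is reported.

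3. Later evaluations may exist. The data sets are pooled, long-term observation runs to 96 weeks, and the PFS definition in SAP 6.2 runs to the final tumour evaluation with no cap at Week 24. A safety objective does not prove that tumour response went uncollected. This is unknown rather than refuted. If such data exist, they exist only for re-registered patients, so qualifying would depend partly on re-registration.

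4. The booklet limits are recording periods, not permitted scan dates. True, and this is a further reason to state an analysis window.

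**Conclusion.** The point holds in a limited form. The 24-week condition in Protocol 7.2.2 and SAP 6.2 has no margin against the scheduled evaluations of the all patient surveillance, and SAP 8.2.7 contradicts it by dropping the duration. The arithmetic is exact. The conclusion about margin assumes that SD is timed from the start of treatment and that no later evaluation is used; timing from the first SD evaluation would be stricter still.

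The number of patients affected cannot be computed. It would be tempting to turn 120 to 210 of 600 into a loss of 20 to 35 percentage points. The documents do not support that: these are patients re-registered or still on drug, not patients with SD; the higher figure is the trial proportion rather than the one assumed here; and the rate is calculated in an analysis set that need not contain 600. The range is a ceiling for the margin problem and not an estimate.

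**What to change.** Use one definition in Protocol 7.2.2, SAP 6.2 and SAP 8.2.7: best response CR or PR, or SD with no PD up to and including the Week 24 evaluation.

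In the SAP, derive the Week 24 evaluation with a stated day convention and an analysis window. One example is Day 168 plus or minus 14 days with Day 1 = start of administration: 168 − 14 = 154 and 168 + 14 = 182, so Days 154-182. Apply it to whatever evaluations were recorded, without altering the booklet periods. State how a patient with SD but no evaluation in the window is classified, since SAP 7 gives no missing-data rule. If the tabulation of any SD is still wanted, give it a different name.

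The cost is a sentence in three places and one derivation, with no new data collection. The downside is that a scan up to two weeks early counts as 24 weeks. The width of the window is the sponsor's choice; a narrower one reduces this at the price of losing more patients to scan timing.

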6.7 Patient summary (reason for discontinuation)

Continuation or discontinuation of the treatment with this drug is determined on the safety evaluation date. When it is determined that the treatment with this drug cannot be continued, the major reason of discontinuance will be selected from the following options and recorded (multiple selection not permitted). Appropriate data will be recorded to the adverse event section of the form when any of the following options is selected: [2] adverse event, [3] abnormal laboratory test value, or [4] patient's death.

- [1] Insufficient clinical effectiveness
- [2] Adverse event
- [3] Abnormal laboratory test value
- [4] Patient's death (date of death)

- [5] Lost to follow-up (reason)
- [6] Others (specify the reason, such as treatment completed because of cure)

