The progress of the target malignant tumor will not be recorded as an adverse event. However, any malignant tumor that reaches a lethal outcome during the observation period has to be recorded as an adverse event. When a patient starts a new treatment, the reportable period of the event will end when the new treatment is started.

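### SAP 6.2 gives PFS two conflicting event windows; read literally, the second counts almost no death without prior progression

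*SAP*

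**What the plan says.** SAP 6.2 item 3 has three parts.

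- **Definition.** PFS runs from treatment start to the first confirmed PD or death from any cause. Two windows are named and joined by 'and': the treatment period with 28 days added, and the period to the final tumour evaluation.
- **Event and censoring rule.** PD or death counts if it falls in the treatment period with 28 days added or in "the period up to the date of final evaluation of tumor response, whichever period is the earlier, will be handled as a PFS event". In addition, "patients without a PFS event will be censored at the date of final evaluation of tumor response".
- **No tumour record.** "Patients with no record on tumor response at all will be censored at the date of initiation of treatment with this drug".

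Protocol 5.4 schedules tumour evaluation at Weeks 8, 16 and 24. For discontinued cases with none in the previous 4 weeks, "clinical evaluation of tumor will be performed at the time of discontinuation". On adverse events it says "If the drug is discontinued before Week 24, observe until Day 28 after the discontinuation of administration".

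SAP 8.1.4 plans Kaplan-Meier quartiles with 95% confidence intervals, and plots. PFS was added in SAP version 3.0. Protocol 7.2.2 names response rate and clinical benefit rate as the main effectiveness items.

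**The concern.** The first sentence names death from any cause as an event. The second closes the window at the earlier of two dates, one of which is the final tumour evaluation. That date reads as the patient's own last evaluation, because the same date is the censoring date for patients without an event. A patient cannot be evaluated after death, so the rule almost removes the death component that the definition names.

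Two programmers could each defend a different curve from this text. One would plot PFS. The other would plot something close to time to documented PD with deaths censored, which looks more favourable because events have become censorings.

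**Working it through.** **Date logic.** Let L be the end of treatment, E the patient's last tumour evaluation and D the date of death, for a death without prior PD in a patient with at least one evaluation.

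1. The literal event rule counts the death if D ≤ min(L + 28 days, E).
2. No evaluation follows death, so E ≤ D.
3. Together these require D = E. Any death even one day after E is censored at E, and the 28-day extension adds no death in these patients.

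An enumeration on a day grid (L weekly over days 0 to 168, E on days 1 to 199, D up to day 259, with L ≤ D and E ≤ D) gave 677,000 combinations. The literal rule counted 724, all with D = E. Taking the later of the two windows would count 73,225.

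**Example.** Stable disease at Weeks 8 and 16, last dose Week 18, death Week 20. The literal window closes at min(18 + 4, 16) = Week 16, so the death is censored at Week 16. Read by the first sentence, with deaths counted to treatment end + 28 days (Week 22), it is an event at Week 20.

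**No tumour record.** A death at Week 5, before any evaluation, is censored at day 0 if the third part is applied to every such patient. It is an event if that part covers only patients without an event, which is the more natural reading.

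**Size, illustration only.** The documents give no PFS figure to reproduce and no rate of death without PD, so every rate here is assumed. The simulation used 400,000 patients per scenario, exponential times and treatment capped at 96 weeks. PD was seen at 8-weekly evaluations, or at discontinuation if there was no evaluation in the previous 4 weeks, with none afterwards. In the base mix (progression 0.03 and other discontinuation 0.03 per week) 49 to 54% are on drug at Week 12 and 19 to 23% at Week 24. The plan assumes 50% (Protocol 3) and 20% (SAP 2.1.2); the 20% also includes loss at re-registration, so the calibration is loose.

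The gap is Kaplan-Meier PFS at Week 24 under the literal window minus PFS with all deaths to treatment end + 28 days counted. Deaths with no tumour record count as events in both. Entries are percentage points at death rates of 0.001 / 0.003 / 0.006 / 0.010 per week.

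| Progression / discontinuation per week | No evaluation entered at death on drug | Evaluation entered on the death date if none in the previous 4 weeks | Evaluation entered at every death on drug |
|---|---|---|---|
| 0.03 / 0.03 | 0.8 / 2.5 / 4.7 / 7.2 | 0.5 / 1.4 / 2.7 / 4.0 | 0.1 / 0.3 / 0.6 / 0.9 |
| 0.02 / 0.04 | 1.1 / 3.3 / 6.4 / 9.7 | 0.7 / 2.0 / 3.8 / 5.7 | within 0.1 to 1.6 |
| 0.04 / 0.02 | 0.6 / 1.8 / 3.5 / 5.4 | 0.4 / 1.0 / 1.9 / 2.9 | within 0.1 to 1.6 |

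In the base mix, these rates mean that 2, 6, 11 and 18% of patients die without PD by treatment end + 28 days. For scale, the 95% half-width at Week 24 with 600 patients is 4.2 to 5.5 points. The gap exceeds it in 4 of 12 scenarios in the first column, 1 of 12 in the second and none in the third.

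The planned quartiles jump on the 8-week evaluation grid. In the base mix, first column, the median is 24 weeks throughout under the literal rule, against 24 / 24 / 22.8 / 16 with deaths counted. No general statement about the quartiles follows.

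**The case against.** The strongest reply is that the first sentence already answers the question. It joins the windows with 'and', has no earlier-of-two rule, and on that reading deaths to treatment end + 28 days count. This stands as evidence of intent, but it leaves the second sentence, which states the event rule, in open conflict with it.

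A reader might infer that the plan plainly discards deaths and that its PFS is materially inflated. The documents do not support that:

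- The effect is zero if the first sentence governs.
- Protocol 5.4 asks for an evaluation at discontinuation, and Protocol 6.7 lists death as a reason for discontinuation without exempting it. An entry on the death date makes D = E, so the death counts. Whether sites make such entries is unknown; if they do, the gap shrinks as the table shows.
- The amendment log places the PFS tabulation in SAP 8.2.7. The visible text there contains none, and some text before Section 9 was removed before review. It may settle the window. The definition in 6.2 would still have to agree with it.

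A reader might also infer that early deaths with no tumour record are censored at treatment start. Applied literally, that would widen the first-column gaps to between 0.9 and 14.1 points, but the sentence more naturally covers patients without an event.

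Finally, PFS is descriptive, is not a main effectiveness item, and belongs to a study that SAP 4 calls non-confirmatory. That limits the consequences. It does not remove the contradiction.

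**Conclusion.** SAP 6.2 item 3 contradicts itself and should be corrected. On the literal event rule, with the final evaluation taken as the patient's own last one, a death without prior PD in an evaluated patient counts only if the last evaluation is dated on the day of death. That conclusion is logical and needs no assumed rates. The bias is upward, towards time to documented PD.

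Its size is not known. Over the assumed death rates and three mixes, the Week 24 gap is about 0.6 to 10 points with no evaluation entered at death on drug, about 0.4 to 6 with the discontinuation evaluation entered on the death date where due, and about 0.1 to 1.6 with one entered at every such death. It is zero if the first sentence governs. The finding covers the visible text only.

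**What to change.** Reconcile the two sentences by replacing the earlier-of-two-periods clause with one explicit cut-off that does not end at the last tumour evaluation.

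- **Cut-off.** For example, treatment end + 28 days, which matches the adverse event observation in Protocol 5.4. SAP 6.1 item 10 foresees patients whose treatment end is not reported; state a cut-off for them too, such as the end of observation.
- **Event.** The first of documented PD or death from any cause on or before the cut-off, on its own date, whether or not a tumour evaluation exists.
- **Censoring.** All others at their last tumour evaluation on or before the cut-off. Limit censoring at treatment start to patients with no tumour record and no death by the cut-off.
- **Reporting.** Give the number of deaths without PD counted as events.

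Under this rule the Week 20 death and the Week 5 death above are both events on their own dates.

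The cost is one SAP paragraph and a small programming change, with these downsides:

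- PFS becomes less favourable than under the literal rule, by an unknown amount.
- PD found after the cut-off is not counted. If the sponsor wants it counted, a later PD cut-off with a matching censoring date must be stated.
- Death dates are only partly covered. The date field in Protocol 6.7 belongs to death as the single permitted reason for discontinuation. Protocol 6.8 requires that "any malignant tumor that reaches a lethal outcome during the observation period has to be recorded as an adverse event", but its item list has onset date and outcome, not a separate date of death. For patients who stop for another reason and die within 28 days, the SAP should name the source of the date.
- Some deaths after a change of therapy may be missed, because "the reportable period of the event will end when the new treatment is started".

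### PFS censors patients who stop for insufficient effectiveness within 4 weeks of a non-PD tumour evaluation, which biases PFS upward by an amount the documents do not fix

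*SAP*

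**What the plan says.** SAP 6.2, item 3, counts PD or all-cause death as the PFS event. For everyone else, "patients without a PFS event will be censored at the date of final evaluation of tumor response". It adds: "Patients with no record on tumor response at all will be censored at the date of initiation of treatment with this drug". The event window refers to treatment plus 28 days and to the time up to the final tumour evaluation. One sentence joins the two periods; the next says that PD or death in one or the other, "whichever period is the earlier, will be handled as a PFS event".

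Protocol 5.4 sets the schedule: "Clinical evaluation of tumor: Weeks 8, 16, and 24". For discontinued cases an evaluation at discontinuation is required "if the clinical evaluation of tumor is not performed within 4 weeks prior to discontinuation". No tumour evaluation is scheduled later. For adverse events, sites must "observe until Day 28 after the discontinuation of administration", but Protocol 6.8 says that non-lethal progression of the target tumour is not recorded as an adverse event.

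Protocol 6.7 records one main reason for stopping, and option [1] is "Insufficient clinical effectiveness". The PFS definition does not use it. SAP 8.1.4 specifies Kaplan-Meier, and SAP 7 (missing data) is marked not applicable.

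**The concern.** Take a patient with SD on Day 56 (Week 8) who stops on Day 77 for reason [1]. The last evaluation is 77 − 56 = 21 days old, so no further one is required, and with no PD on record PFS is censored at Day 56. The physician has judged that the drug is not working, yet the analysis treats the patient as having the same later risk as those who stay on treatment.

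Kaplan-Meier needs censored and retained patients to have the same later risk. When patients near progression leave the risk set as non-events, the curve is too high. Confirming effectiveness under actual use is part of the first objective, and the final analysis supports the re-examination application. Protocol 3 assumes that 50% of patients, for all reasons together, will have stopped by Week 12, so the handling of stops affects the early part of the curve.

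**Working it through.** **Plan's own figure.** The documents give no PFS median, event count or precision target, so there is no PFS figure to reproduce. The registration target does reproduce: 300 / (1 − 0.5) = 600. It has no bearing on PFS.

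**Who is exposed.** With evaluations every 8 weeks and the 4-week rule, a clinical stop in the first half of an interval that follows an evaluation needs no new evaluation. A stop in the second half does.

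**Assumptions (not in the documents).** Progression is exponential with median m weeks. A fraction f of progressors is stopped on clinical grounds at the moment of progression. Every required discontinuation evaluation is done and shows PD. The remaining progressors are detected at the next scheduled evaluation. Stops in the first 4 weeks are taken as evaluated.

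**Share of clinical stops exposed.** Let q = 2^(−4/m), the chance of staying progression-free for 4 weeks. The share of clinical stops falling within 4 weeks after a scheduled evaluation is q²/(1 + q).
- m = 12: 0.630/1.794 = 35%
- m = 16: 0.707/1.841 = 38%
- m = 24: 0.794/1.891 = 42%

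**Effect on 24-week PFS.** True PFS is q⁶. Just after Week 8, and again just after Week 16, a fraction c = f(1 − q) of those at risk is censored although about to progress. Each of those two interval survival factors becomes q²/(1 − c), so the estimate is q⁶/(1 − c)².

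For m = 16, q = 0.8409 and true PFS is 0.8409⁶ = 35.4%:

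| f | c | Estimated 24-week PFS | Overstatement |
|---|---|---|---|
| 10% | 0.0159 | 0.3536/0.9841² = 36.5% | 1.2 points |
| 25% | 0.0398 | 0.3536/0.9602² = 38.3% | 3.0 points |
| 50% | 0.0796 | 0.3536/0.9204² = 41.7% | 6.4 points |

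**Simulation.** A run of 200,000 patients per scenario added independent other stops at 0.02 per week and 8-weekly evaluations to Week 96. It compared the plan's rule with counting the clinical stop as a failure at the stop date.

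| Median (weeks) | f = 10% | f = 25% | f = 50% |
|---|---|---|---|
| 12 | 25.9% vs 24.8% | 27.7% vs 24.8% | 30.9% vs 24.6% |
| 16 | 36.6% vs 35.4% | 38.6% vs 35.4% | 41.8% vs 35.0% |
| 24 | 51.2% vs 50.0% | 52.8% vs 49.9% | 55.7% vs 49.6% |

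The plan's rule is higher in every cell, by about 1 to 7 points. At m = 16 the patients whose status changes from event to censored are 2.3%, 5.8% and 11.7% of all patients for the three values of f.

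**If required evaluations are missed.** Suppose, as a further assumption, that 30% of the required discontinuation evaluations are not done, including those for stops before Week 8, and that those patients are censored at the previous evaluation or at treatment start. For m = 16 the overstatement becomes about 2, 5 and 10 points. At f = 50%, the fraction lost after Weeks 8 and 16 is 0.5 × (0.1591 + 0.3 × 0.8409 × 0.1591) = 0.0996, and in the first interval it is 0.5 × 0.3 × 0.2929 = 0.0439. The estimate is 0.3536/(0.9004² × 0.9561) = 45.6%, against 35.4%.

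**The 28-day window.** In the Day 56/Day 77 example, treatment plus 28 days ends on Day 105 and the period to the final evaluation ends on Day 56. If either period suffices, PD or death up to Day 105 counts. If the earlier period governs, nothing after Day 56 counts, not even a death. The first reading recovers some events; the second adds to the upward bias.

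**The case against.** The strongest reply is that counting only documented PD or death is a legitimate definition, in a surveillance study that SAP 4 calls non-confirmatory, and that no visible decision rests on PFS. That stands, and it is why the main definition need not change.

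Reason [1] also does not by itself mean undocumented progression. Protocol 6.7 offers no separate option for disease progression, so patients with recorded PD may well be coded [1]; they are already PFS events. Only reason [1] stops without recorded PD matter here, and their number is unknown.

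A PFS tabulation was added to SAP 8.2.7 according to the SAP's amendment table, but that text was not available for review. An existing sensitivity analysis there cannot be excluded. SAP 8.2.4 already tabulates reasons for discontinuation, though it does not link them to PFS censoring.

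Three stronger readings are tempting and not supported:
- **Every clinical stop is censored at the previous evaluation.** For m = 16 that would give 24-week PFS of [q²/(1 − f(1 − q²))]³, or 39%, 42% and 47% for f = 10%, 20% and 30%. Protocol 5.4 rules this out by requiring an evaluation when the last is more than 4 weeks old. With that rule the figures are about 36.5%, 38% and 39%. If a pre-treatment evaluation also exempted stops in the first 4 weeks, f = 20% would give 0.3536/0.9682³ = 39.0%, still below 42%.
- **80% will have stopped by Week 24, so most of the curve depends on this rule.** SAP 2.1.2 reaches 80% partly by allowing for re-registration into the long-term study; the trials' figure was about 65%. Both cover all reasons for stopping.
- **The median moves by a whole evaluation interval.** It did for medians of 16 and 24 weeks, but those values put 50% survival exactly on an evaluation date. At 12 weeks it did not move.

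**Conclusion.** The concern holds in a limited form. The visible rules censor, at an earlier non-PD evaluation, patients stopped for insufficient effectiveness within 4 weeks of it, unless PD or death is picked up in the 28-day window. The bias is upward.

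Its size cannot be derived from the documents. Under the stated assumptions, 24-week PFS is overstated by about 1 to 7 points. The upper end needs half of all progressors to be stopped on clinical grounds, and larger values need required evaluations to be missed. The conclusion rests on reason [1] stops being closer to progression than other patients at risk, and on there being no relevant rule in the unavailable part of SAP 8.2.7. This is an inexpensive improvement to a secondary analysis and does not invalidate the study.

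**What to change.** Keep the main PFS definition in SAP 6.2. Unless the unavailable part of SAP 8.2.7 already does so, add a prespecified sensitivity analysis in which a stop for reason [1] without recorded PD is an event on the discontinuation date. Report 8-, 16- and 24-week PFS from both versions, and the number censored by reason for discontinuation. In the same edit, state whether the 28-day window and the period to the final evaluation are combined or the earlier one governs.

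The cost is SAP wording, one extra Kaplan-Meier run and one table, all from data already on the case report form. The drawback is that some reason [1] stops are not true progression, so the sensitivity result may be pessimistic. The two versions show how far PFS depends on the rule. They are not guaranteed bounds, because stops for adverse events or loss to follow-up stay censored in both.
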